### 3.10 Long Term Safety Outcomes (1 Year)

- a. Stroke
- b. Transient ischemic attack
- c. Major vascular complications
- d. Renal complications

### 4. ANALYSIS POPULATIONS

### 4.1 Enrolled Population

Any patient who has signed informed consent will be included as part of the enrolled population. Should a patient be considered ineligible after signing consent and before randomization, the reason for failure will be documented, and the patient will be exited from the study. For roll-in patients, the enrolled population will be based on those who signed informed consent, met eligibility criteria, and had the procedure attempted. Serious adverse events (SAEs) will be reported for all enrolled patients through study exit.

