6.1 Patient Population

Adult patients age \geq 18 years at time of screening with primarily functional MR (\geq 3+) and symptomatic heart failure despite guideline directed medical therapy (GDMT) should be considered for inclusion in this trial. Patient will be considered enrolled in the study at the time written informed consent form (ICF) is signed and will be assigned a patient ID in the electronic data capture (EDC) system. Patients that sign the ICF, but are found ineligible during the screening process, will be considered screen failures. Screen failures will not be counted towards enrolled roll-in patients or the pre-planned sample size (i.e., the enrollment will continue until the pre-planned 375 non-screen failures are enrolled). If a patient is identified as a screen failure during the index procedure (prior to placement of the system into the body), the patient shall be followed for 30 days for the purposes of safety evaluations only and will be reported upon as a separate Screen Failure cohort safety analysis.

In studied populations the average age of patients with mitral regurgitation is 67 (± 12.7) years⁴. This study is expected to enroll patients with baseline characteristics (e.g. age) similar to previously studied populations, and results are expected to be generalizable to individuals qualifying for Medicare based on age criteria.

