13.3 Analysis Populations

13.3.1 Enrolled Population

Any patient who has signed informed consent will be included as part of the Enrolled Population. Should a patient be considered ineligible after signing consent and before randomization, the reason for failure will be documented, and the patient will be exited

from the study. Serious adverse events (SAEs) will be reported for all enrolled patients through study exit.

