13.4.6 Adverse Events Analyses

Adverse events (AE) will be summarized by treatment for the FAS population and mITT and AEs will be summarized by severity and relatedness. Serious AEs will be presented in a listing.

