#### 2.2 **Overall Study Design and Plan**

This study is a prospective, randomized, multicenter clinical evaluation of the Edwards Cardioband System for the treatment of clinically significant functional mitral regurgitation in MR patients who are treated in accordance with current ACC/AHA valve guidelines. The study design incorporates a roll-in cohort to provide experience in use of the Edwards Cardioband System prior to randomizing patients into the pivotal study cohort at a given investigational site. The roll-in cohort will include a maximum of three patients per site (e.g. if 75 sites used, a maximum of 225 roll-in patients). Data for the roll-in patients will be presented and analyzed as a separate cohort. All patients are followed for 30 days, 6 months, 1 year, and annually for a total of five years post-index procedure or randomization in the case of the Control population.

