### 4.2 Intent-to-Treat Population (Safety Analysis)

The intent-to-treat population (ITT) will consist of all patients who have signed informed consent and have been randomized. Patients that have entered the procedure room but have not received an implant attempt (passing of any Edwards Cardioband System component past the skin) will be deregistered and followed through 30 days for safety purposes only.

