### 9.2 Adverse Events

Site reported and CEC adjudicated adverse events will be descriptively summarized in tables and listings for the ITT population. MedDRA codes will be provided in addition to seriousness, relation to device, and relation to procedure. Both patient and event counts will be summarized.

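### If SAP 4.1 means eligibility in fact, a roll-in patient treated despite an eligibility violation is guaranteed a place in no defined analysis set or safety table

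*SAP*

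**What the plan says.** Protocol 13.3.1 sets a broad rule: "Any patient who has signed informed consent will be included as part of the Enrolled Population". It reports SAEs for all of those patients through study exit.

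SAP 4.1 opens with the same rule but adds an exception: "For roll-in patients, the enrolled population will be based on those who signed informed consent, met eligibility criteria, and had the procedure attempted". The next sentence is "Serious adverse events (SAEs) will be reported for all enrolled patients through study exit". SAP section 10 discloses the new roll-in definition as the only difference from protocol rev E. Its reason is that the definition is more useful for evaluating the device and procedure, and it is to enter future protocol updates.

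The other places where safety is reported are these:

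- SAP 4.2: "The intent-to-treat population (ITT) will consist of all patients who have signed informed consent and have been randomized".
- SAP 9.2: "Site reported and CEC adjudicated adverse events will be descriptively summarized in tables and listings for the ITT population".
- Protocol 13.4.6: "Adverse events (AE) will be summarized by treatment for the FAS population and mITT".
- Protocol 6.1: "Patients that sign the ICF, but are found ineligible during the screening process, will be considered screen failures". It also recognises screen failure during the index procedure, but only before the system is placed in the body. SAP 4.3 promises a safety summary of all screen failures.
- SAP 2.2: "Data for the roll-in patients will be presented and analyzed as a separate cohort". No population or safety table is named for that presentation.

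**The concern.** Roll-ins are each site's first implants, so their safety record describes the learning curve. A safety set for that purpose should be fixed by exposure: consent was given and the procedure was attempted. An eligibility condition can remove a patient after exposure, for a reason that may be linked to risk. If patients treated outside the criteria have more events, the roll-in event rate looks better than it was.

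The reason given in SAP 10 supports requiring an attempted procedure. It does not support leaving out attempted patients who proved ineligible, because their procedures inform device and procedure safety just as much.

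The attempt condition has its own side effect. Adverse events are collected from consent (Protocol 6.6), so SAEs can occur during work-up in a patient who never reaches the procedure.

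**Working it through.** **1. The plan's own figures.** The maximum is 3 roll-ins per site at 75 sites: 3 × 75 = 225. Adding the pivotal cohort, 375 + 225 = 600. Both match Protocol section 4 and SAP 2.4. No stated figure is wrong; the question is who falls in which set.

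**2. Two roll-in patients traced through every defined set.** Patient A consented, had the procedure attempted, and is later found to have violated a criterion. Patient B consented and was eligible, had an SAE during work-up, and never had the procedure attempted.

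| Set or output | Rule | A | B |
|---|---|---|---|
| Protocol 13.3.1 Enrolled | consent | in | in |
| SAP 4.1 Enrolled, roll-ins | consent, eligibility and attempt | out if eligibility is in fact; in if it means prior approval | out |
| SAP 4.2 ITT | randomized | out | out |
| SAP 4.3 mITT | drawn from randomized patients | out | out |
| SAP 4.4 Device Implant | subset of mITT | out | out |
| SAP 9.2 AE tables | ITT | out | out |
| Protocol 13.4.6 AE summaries | FAS and mITT | out | out |
| Screen-failure summary | ineligibility found in screening, or before the system enters the body | not clearly covered | out (eligible) |
| Separate roll-in presentation, SAP 2.2 | no population or table named | not guaranteed | not guaranteed |

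Patient A's place depends on how one undated phrase is read. Patient B loses the protocol's SAE reporting on either reading.

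**3. How many patients like A.** The documents give no violation rate, so v is assumed. With N treated roll-ins, the expected number is N × v. Treating patients as independent, the chance of at least one is 1 − (1 − v)^N.

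| v (assumed) | N = 225: expected | N = 225: P(at least one) | N = 75: expected | N = 75: P(at least one) |
|---|---|---|---|---|
| 1% | 2.25 | 0.896 | 0.75 | 0.529 |
| 2% | 4.5 | 0.989 | 1.5 | 0.780 |
| 5% | 11.25 | >0.999 | 3.75 | 0.979 |
| 10% | 22.5 | >0.999 | 7.5 | >0.999 |

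N = 225 is the ceiling. N = 75 shows a smaller cohort, for example one treated roll-in at each of 75 sites.

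**4. Effect on a reported roll-in event proportion (illustration only).** Assume a 10% event rate in eligible patients and a rate r in violators. The rate in all treated roll-ins is (1 − v) × 0.10 + v × r, against 0.10 in the eligible-only set.

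- v = 2%, r = 30%: 0.98 × 0.10 + 0.02 × 0.30 = 10.4%.
- v = 5%, r = 30%: 0.95 × 0.10 + 0.05 × 0.30 = 11.0%.
- v = 10%, r = 30%: 0.90 × 0.10 + 0.10 × 0.30 = 12.0%.
- r = 10% at any v: 10.0%, no bias.

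Under these assumptions the understatement runs from nothing to 2 percentage points.

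**The case against.** The strongest reply is that the phrase has no time point. The Central Screening Committee reviews each patient before enrolment, and only approved cases are scheduled (Protocol section 4 and the committee determination before section 7). The three conditions in SAP 4.1 may simply list those steps in order. Protocol 6.1 likewise keeps screen failures out of the roll-in count. On that reading, an approved and attempted patient stays in the set when a violation surfaces later. This stands as a possible reading, and the point about treated violators is conditional for that reason. It does not defend the wording: if eligibility means prior approval, the condition adds almost nothing to an attempted procedure and can be deleted without loss.

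A reader might infer that treated violators appear in no safety table at all. The documents do not establish that. The separate roll-in presentation carries no stated eligibility limit, Protocol 15.4.1 describes roll-ins as patients who undergo the procedure, and neither text clearly excludes such a patient. What is missing is a guarantee.

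It is also fair that the SAP 9.2 tables leave out every roll-in patient, eligible or not. Deleting the eligibility condition alone would not create a roll-in table, so the fix has to name one.

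A contrast with the randomized cohort is tempting but not clean. Protocol section 7 keeps a patient who becomes ineligible as randomized, yet the note in Protocol 8.2 withdraws a patient found ineligible before the procedure and does not count that patient toward the sample size. The point does not rest on this comparison.

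Finally, oversight does not depend on SAP 4.1. Apart from the expected events listed in Protocol 11.4, all adverse events go on the eCRF, SAEs go to the sponsor within 3 calendar days, and CEC and DSMB review continue. This stands and limits the point to reporting.

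**Conclusion.** The point holds as a gap in the reporting rule. SAP 4.1 attaches an eligibility condition to the only defined population that contains roll-ins and carries SAE reporting, and no other defined set or table is certain to cover a treated violator. This part assumes that eligibility is judged in fact; under a prior-approval reading it falls away. The loss of SAE reporting for eligible, consented roll-ins whose procedure is never attempted holds on either reading.

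The size is unknown. About 2 to 23 of 225 patients follows from an assumed 1% to 10% violation rate and the maximum cohort. Any bias also requires violators to have more events than eligible patients, which the documents do not show.

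Two further inferences are not supported. One is that a reported roll-in MAE rate would be understated: the MAE endpoint is for the randomized Device group, and no roll-in MAE table is defined. The other is that the change was concealed: SAP 10 states it openly. No primary efficacy or safety result changes. The amendment is worth making because it is harmless under one reading and prevents exclusion after exposure under the other.

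**What to change.** In SAP 4.1:

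- Delete the eligibility condition, so that the roll-in procedure and safety set is all consented roll-in patients with an attempted procedure, whatever their eligibility. Use the notion of attempt already in SAP 4.2, that is, any system component passed beyond the skin.
- State that the roll-in AE and SAE tables use this set, and list those tables.
- Keep SAE reporting for every consented roll-in patient, attempted or not, as in Protocol 13.3.1.

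Because SAP 10 says the definition will move into a future protocol update, correct it before then.

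The cost is a few sentences and the named tables. No new data are needed, since adverse events are already collected from consent. The downside is that the reported roll-in event rate may be slightly less favourable.

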### 4.2 Intent-to-Treat Population (Safety Analysis)

The intent-to-treat population (ITT) will consist of all patients who have signed informed consent and have been randomized. Patients that have entered the procedure room but have not received an implant attempt (passing of any Edwards Cardioband System component past the skin) will be deregistered and followed through 30 days for safety purposes only.

### 4.3 Modified Intent-to-Treat Population (Efficacy Analysis)

The modified intent-to-treat population (mITT) will consist of all patients randomized to the Control Group and all patients randomized to the Device group that have had the Edwards Cardioband System implanted. The mITT population represents the primary analysis population for this study. The randomization will continue until 375 mITT patients are enrolled.

THIS DOCUMENT CONTAINS CONFIDENTIAL AND PROPRIETARY INFORMATION OF EDWARDS LIFESCIENCES, LLC. IT MUST NOT BE REPRODUCED OR DISCLOSED TO THIRD PARTIES WITHOUT PRIOR WRITTEN PERMISSION OF EDWARDS LIFESCIENCES, LLC. (This template is required by DOC.))

E	Revision Date: February 28, 2019		Rev		For Use Only by Affiliates of Edwards Lifesciences	Page 9 of 18
Edwards	Title	Statistical Analysis Plan	for	ACTIVE	2017-05	

A separate summary of the safety on all screen failure patients shall be provided as part of the study final report.

### 4.4 **Device Implant Population**

The device implant population is defined as the subset of the mITT population consisting of those patients for whom any part of the Edwards Cardioband System is implanted and remains in position (i.e., absence of any anchor detachment). This population will be utilized as a secondary analysis population.

### 5. **DEFINITIONS**

### 5.1 Analysis Dates and Days

- Study start date is defined as the procedure date.
- Last information date is defined as the most recent date assessed with any available information concerning the patient (e.g., most recent date out of: baseline assessment, procedure, discharge, follow-up visits, laboratory tests, study termination, and adverse events). Last information date is used as censor date for survival analyses.
- Study day = Date Study start date

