Randomization is ideally performed within seven days prior to the scheduled procedure, but no more than 14 days prior. If a patient is randomized to control, the scheduled interventional case is cancelled and the patient is notified that they have been enrolled in the control/medical therapy arm of the trial and will not need to undergo an interventional procedure. The process of randomizing after a case is scheduled has been implemented to ensure that the time frame between randomization and actual treatment is minimized. As depicted in the flowchart, all

patients are followed for 30 days, 6 months, 1 year and annually for a total of 5 years post-index procedure or randomization in the case of the control population.

[figure not shown]

Figure 4: Clinical Study Design Flowchart

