Patients with a documented intolerance to Guideline Directed Medical Therapy (GDMT) will be eligible for study inclusion. All patients (i.e. whether assigned to Device and Control groups) shall continue to receive stable Guideline Directed Medical Therapy as directed by current heart failure guidelines (including use of cardiac resynchronization therapy, as indicated).^{27,28} This implies that the GDMT regimen in principle remains unchanged until primary efficacy endpoint, unless medically warranted. Changes to GDMT (doubling or halving of dose) will be documented including whether these occurred due to improvement, deterioration, or no change in the patient's condition. Medical management should continue under the direction of a heart failure specialist at regular intervals according to current heart failure guidelines.^{27,28}

FOLLOW-UP EVALUATIONS

Follow-up evaluations will be scheduled for 30 days, 180 days, 1 year, 2 years, 3 years, 4 years, and 5 years.

- For patients assigned to the Device group, the follow-up visits are scheduled based on the date of the Edwards Cardioband System index procedure.
- For patients assigned to the Control group, the follow-up visits are scheduled based on the date of randomization.
- Note: A patient in the Control group may be offered an opportunity to receive an Edwards Cardioband System after they have been followed for a minimum of 1 year and completed their primary efficacy endpoint assessment. At the time of their 1 year follow-up visit, if the patient chooses to receive the investigational device, they will be evaluated in accordance with the eligibility criteria (including concurrence by the site Heart Team and the CSC). If the patient is still eligible for enrollment, he/she will be offered an opportunity to receive the device. If the patient receives the Edwards Cardioband System implant, he/she shall be followed in accordance with the clinical

protocol schedule or at a minimum for two years if the product has received PMA Approval. This group shall be summarized as a separate cohort.

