The 6MWT distance at baseline and 1 year will be quantified as continuous variables measured in meters and the difference between the two time points will be calculated. This difference in distance (i.e., delta) will be analyzed with T statistic with a two-sided alpha of 0.05. The null (H_0) and alternative (H_A) hypotheses are:

 H_0 : $\Delta_{CardB} = \Delta_{Control}$

 H_A : $\Delta_{CardB} \neq \Delta_{Control}$

 Δ_{CardB} and $\Delta_{Control}$ represent mean deltas for the Device and Control groups, respectively.

36-Item Short Form Survey (SF-36)

SF-36 score at baseline and 1 year will be quantified as continuous variables ranging from 0 to 100 and the difference between the two time points will be calculated. This difference (i.e., delta) will be analyzed with T statistic with a two-sided alpha of 0.05. The null (H_0) and alternative (H_A) hypotheses are:

 H_0 : $\Delta_{CardB} = \Delta_{Control}$

 H_A : $\Delta_{CardB} \neq \Delta_{Control}$

 Δ_{CardB} and $\Delta_{Control}$ represent mean deltas for the Device and Control groups, respectively.

Heart Failure Hospitalizations

The number of heart failure hospitalizations between day 0 and day 365 post procedure will be quantified as recurrent events and analyzed with a survival analysis intensity model.³⁰ The null (H₀) and alternative (H_A) hypotheses are:

 H_0 : HR = 1

 H_A : $HR \neq 1$

HR represents hazard rates for Device group relative to Control group, respectively. Two-sided alpha of 0.05 will be used.

Cardiovascular Mortality

PROTOCOL NUMBER: 2017-05

Cardiovascular mortality rate up to 365 days will be compared between the Device and Control groups using time-to-event analysis and log-rank test. The null (H₀) and alternative (H_A) hypotheses are:

 $H_0: HR = 1$

H_A: HR ≠ 1

HR represents hazard rates for Device group relative to Control group, respectively. Two-sided alpha of 0.05 will be used.

All-Cause Mortality

All-cause mortality rate up to 365 days will be compared between the Device and Control groups using time-to-event analysis and log-rank test. The null (H₀) and alternative (H_A) hypotheses are:

 H_0 : HR = 1

H_Δ: HR ≠ 1

HR represents hazard rates for Device group relative to Control group, respectively. Two-sided alpha of 0.05 will be used.

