### 2017-05 Statistical Analysis Plan |

| 1.0 | 7/16/2019

Edwards	Revision Date: February 28, 2019		Rev		For Use Only by Affiliates of Edwards Lifesciences	Page 12 of 18
	Title	Statistical Analysis Plan for ACTIVE 2017-05				

#### Table 1. Hierarchy of co-primary endpoints 2

Comparison of each potential patient pair	How Event is
(e.g. 1 from Device group and 1 from Control group)	Assessed
Step 1	
If 1 or both patients die due to cardiovascular (CV) cause	
Patient in Device group dies first due to CV cause	Favors Control
Patient in Control group dies first due to CV cause	Favors Device
Both patients die on the same day due to CV cause	Go to Step 2
If neither of the patients die due to CV cause	Go to Step 2
Step 2	
If no ranking yet available	
Patient in Device group had more heart failure hospitalizations	Favors Control
Patient in Control group had more heart failure hospitalizations	Favors Device
Both patients had equal number heart failure hospitalizations	Go to Step 3
Step 3	
If no ranking yet available	
Patient in Device group but not patient in Control group improved 6 minutes walking	Favors Davisa
distance ≥ 40 meters compared to baseline	Favois Device
Patient in Control group but not patient in Device group improved 6 minutes walking	Favors Control
distance ≥ 40 meters compared to baseline	
Both patients improved 6 minutes walking distance ≥ 40 meters compared to baseline	Go to step 4
Neither of the patients improved 6 minutes walking distance ≥ 40 meters compared to	Go to step 4
baseline	
Step 4	
If no ranking yet available	
Patient in Device group (but not Control) improved KCCQ score ≥10 points compared to	Eavors Device
baseline	Favois Device
Patient in Control group (but not Device)improved KCCQ score ≥10 points compared to	Favors Control
baseline	
Both patients improved KCCQ score ≥10 points compared to baseline	Tie
None of the patients improved KCCQ score $\geq 10$ points compared to baseline	Tie

The following rules are applied with the pairwise comparative outcome assessment:

- If any one of the patients in a patient pair is missing data for a variable included in the hierarchy then the pair will be considered a tie in regards to that variable/level and will proceed to the next level in the hierarchy.
- The time dependent events are censored at exactly 1 year after randomization.

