### f. Heart Failure Hospitalizations

The number of heart failure hospitalizations between day 0 and day 365 post procedure will be quantified as recurrent events and analyzed with a survival analysis intensity model (Andersen and Gill, 1982). The null ( $H_0$ ) and alternative ( $H_1$ ) hypotheses are:

H0: HR = 1 H1: HR ≠ 1

HR represents hazard rate for Device group relative to Control group. A two-sided alpha of 0.05 will be used.

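### Study day 0 is the procedure date, which Control patients lack, so the gated heart failure hospitalization test starts at treatment in Device and at randomization in Control

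*SAP*

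**What the plan says.** - SAP 5.1: "Study start date is defined as the procedure date". Study day is counted from that date, and the same section sets the censoring date for survival analyses. It has no rule for a patient without a procedure.
- SAP 8.4f, the sixth key secondary endpoint: "The number of heart failure hospitalizations between day 0 and day 365 post procedure will be quantified as recurrent events". Protocol 13.4.4 uses the same window: "The number of heart failure hospitalizations between day 0 and day 365 post procedure".
- SAP 8.4g and 8.4h, and the matching parts of Protocol 13.4.4, limit cardiovascular and all-cause mortality to 365 days without saying from when.
- SAP 8.2, pairwise rules for co-primary II: "The time dependent events are censored at exactly 1 year after randomization". Protocol 13.4.2 has the same rule. It applies to both arms.
- Protocol section 9: "For patients assigned to the Device group, the follow-up visits are scheduled based on the date of the Edwards Cardioband System index procedure", and "For patients assigned to the Control group, the follow-up visits are scheduled based on the date of randomization". SAP 2.2 likewise runs follow-up for "five years post-index procedure or randomization in the case of the Control population".
- Protocol section 4: "Randomization is ideally performed within seven days prior to the scheduled procedure, but no more than 14 days prior".
- SAP 4.3 defines the efficacy population (mITT) as all randomized Control patients, but only those Device patients who were implanted.
- SAP section 10 names the roll-in enrolled-population definition as the only departure from the protocol, so it does not settle the origin.

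**The concern.** A between-arm comparison of event counts needs one origin that exists for every randomized patient. SAP 5.1 gives an origin that Control patients do not have, and the hospitalization test depends on it. The programmer must therefore supply a Control day 0. The only candidate in the documents is randomization, which puts the arms of an alpha-gated test on different origins.

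Two things follow. The same hospitalization is treated differently by two confirmatory tests, depending on the arm. And Device time at risk begins after a waiting period that the Control clock includes. That period may not be neutral: several exclusion windows in Protocol 6.3 are tied to the procedure date, and Protocol 8.2 withdraws a patient found ineligible between randomization and the procedure.

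**Working it through.** **1. Which events count.** Take a Device patient who is later implanted, a 14-day wait, and Control starting at randomization. The Device window after the procedure ends at day 14 + 365 = 379 after randomization.

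| Heart failure hospitalization | Co-primary II | Key secondary 6 |
|---|---|---|
| Device, between randomization and implant | counted | not counted |
| Device, days 366 to 379 after randomization | not counted | counted |
| Control, first 14 days after randomization | counted | counted |
| Control, after day 365 | not counted | not counted |

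**2. Planned rates (Protocol 13.5, SAP 8.11).** With five or more counted as 5, the yearly means per patient are:
- Control: 0.10×1 + 0.10×2 + 0.10×3 + 0.05×4 + 0.05×5 = 1.05
- Device: 0.10×1 + 0.05×2 + 0.05×3 + 0.05×4 + 0.05×5 = 0.80
- Ratio: 0.80/1.05 = 0.76

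The plan gives no figure for the effect of the wait. The nearest stated figure is the power of co-primary II with 300 evaluable patients: above 90% in the synopsis, 87% in Protocol 13.5 and SAP 8.11. A simulation of the SAP 8.2 score test at these rates gave 93.5% with the walk-test and KCCQ responses independent. It gave 84.8% when the KCCQ response copied the walk-test response in half the patients. The inputs are therefore consistent with the plan.

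**3. Device hospitalizations in the wait.** The 375 mITT patients at 2:1 give 250 Device and 125 Control. Events spread evenly over the year give n × rate × days/365:
- Device at 0.80: 250×0.80×7/365 = 3.8; at 14 days, 7.7 (of 200 a year)
- Device at the untreated rate of 1.05: 250×1.05×7/365 = 5.0; at 14 days, 10.1
- Control in the same interval, counted: 125×1.05×7/365 = 2.5; at 14 days, 5.0

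The wait is 7/365 = 1.9% to 14/365 = 3.8% of the year.

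**4. Effect on the rate ratio.** With a full 365 days from each arm's own day 0 and constant hazards, the planned ratio is 0.76. On a common randomization clock with a 14-day wait at the untreated rate, the Device rate is (14×1.05 + 351×0.80)/365 = 0.81, and 0.81/1.05 = 0.77. If the true ratio is 1, it does not move.

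**5. Deaths and the population.** At 20% one-year mortality and constant hazard, 250×(1 − 0.8^(7/365)) = 1.1 Device deaths fall in a 7-day wait, and 2.1 in a 14-day wait. These patients are never implanted, so mITT excludes them whichever date is day 0.

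**6. Changing the clock but keeping mITT.** A log-rank simulation with no true effect (250 against 125, 20,000 trials) let no Device patient die before implant and ran time from randomization.

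| Wait | Mean estimated hazard ratio | False significance favouring Device |
|---|---|---|
| none | 1.00 | 2.7% |
| 7 days | 0.98 | 3.4% |
| 14 days | 0.96 | 4.0% |

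**The case against.** The strongest reply is that SAP 2.2 and Protocol sections 4 and 9 already give Control its origin, so SAP 5.1 merely omits half of a known rule. The scheduled wait is short, separate 365-day windows estimate the same rates under constant hazards, and the tests concerned are sixth to eighth in the hierarchy, below both co-primaries. All of that stands, and it limits the severity. It does not remove the problem: reading the Control rule across is what puts the arms on different origins, and a window counted after a procedure remains undefined for Control as written.

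A reader might also infer more than the documents support:
- *Co-primary II compares events on different clocks.* It does not. Its time-dependent events run from randomization in both arms. Only the walk-test and KCCQ visits are scheduled from different dates, within a window of ±45 days.
- *The mortality tests start at the procedure.* SAP 8.4g and 8.4h do not say so. That origin is inferred from SAP 5.1.
- *The clock hides early Device deaths.* The mITT definition removes them under any clock.
- *The error favours Device.* If waiting-time events were dropped while time still ran from randomization, 14 days would turn a true ratio of 1.00 into 351/365 = 0.96, and the planned 0.76 into 0.73. The planned window moves both events and time to the procedure, so these figures do not describe it.

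**Conclusion.** The point holds for the hospitalization test: its origin cannot be applied to Control as written and, completed from the rest of the documents, differs between the arms. It also makes co-primary II and key secondary 6 disagree on the same Device event. For the two mortality tests, the defect is an unstated origin.

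The expected size is small: about 4 to 10 Device hospitalizations in the wait, and a rate-ratio shift of about 0.01 at 14 days. This rests on constant hazards, events spread evenly over the year, five or more counted as 5, and a wait of at most 14 days. That limit applies to the scheduled procedure, so a postponement would lengthen the wait. The effect could also grow if risk differs during the wait; its direction is not established. The plan should be corrected because a confirmatory test lacks a usable common origin, not because a large bias is expected.

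**What to change.** - In SAP 5.1, define day 0 as the randomization date in both arms for all between-arm time-to-event and event-count analyses. Keep the procedure date as day 0 for Device-only endpoints (30-day major adverse events; device, procedural and clinical success).
- In SAP 8.4f and Protocol 13.4.4, count hospitalizations from randomization to day 365. State the same origin in SAP 8.4g and 8.4h and in the mortality parts of Protocol 13.4.4.
- Run 8.4f to 8.4h on that clock in all randomized patients (ITT). A change of clock alone, within mITT, would give Device guaranteed survival to implant.

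The cost is SAP and protocol wording, one derived date and an ITT run of three tests. Device estimates may become slightly less favourable. One limit needs stating: SAP 4.2 deregisters patients who enter the procedure room without an implant attempt and follows them for 30 days only. Protocol section 7 still regards patients who become ineligible after randomization as randomized. The ITT run must say how such patients are handled.
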